- 2 = Moderate (more prominent red color of the palpebral or bulbar conjunctiva).
- 3 = Severe (definite redness of palpebral or bulbar conjunctiva).

Lens

- 0 = No opacification (normal lens).
- 1 = Mild lens opacification.
- 2 = Moderate lens opacification.
- 3 = Severe lens opacification.

Iris

- 0 = Normal
- 1 = Abnormal.

Anterior Chamber Inflammation

- 0 = None (no Tyndall effect).
- 1 = Mild (Tyndall effect barely discernible).
- 2 = Moderate (Tyndall beam in the anterior chamber is moderately intense).
- 3 = Severe (Tyndall beam in the anterior chamber is severely intense).

All grading assessments of different eye structures will be evaluated as collected on the eCRF at Baseline Visit, Week 4, Week 8 and Week 12. No imputation will be envisaged for these parameters.

No aggregated presentation is planned for other assessments done during Slit lamp evaluation.

External ocular examination

External Ocular Examination assesses the motility of the extraocular muscles and the appearance and function of the eyelids before the instillation of any dilating or anesthetic eye drops.

Motility of extraocular muscle and appearance/function of eye lids is assessed separately for each eye at Baseline, Week 4, Week 8 and Week 12 visit and is recorded on the eCRF pages 'External Ocular Examination' and 'Appearance and Function of Eyelids'.

For the analysis, the Motility of the Extraocular Muscle will be evaluated by the field of movements Right and up ('Normal', 'Abnormal'), Right ('Normal', 'Abnormal'), Right and Down ('Normal', 'Abnormal'), Left and Up ('Normal', 'Abnormal'), Left ('Normal', 'Abnormal'), Left and Down ('Normal', 'Abnormal') as documented at the eCRF at Baseline Visit, Week 4, Week 8 and Week 12. No imputation will be envisaged for these parameters.

Appearance and Function of Eyelids will be summarized by the following parameters:

- Incidence of proven eyelid deformity/abnormality, which will be considered as present, if the question 'Evidence of eyelid deformity or abnormality' on the eCRF page 'Appearance and Function of Eyelids' is answered 'Yes'.
- Incidence of abnormal motor function of eyelids (i.e. upper lid elevation and forceful lid closure), which will be considered as present, if the question 'Motor function of eyelids' on the eCRF page 'Appearance and Function of Eyelids' is answered 'ABNORMAL'.

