- Incidence of corneal exposure in case of closed eyelids, which will be considered as present, if the question 'Is there corneal exposure when the eyelids are closed?' on the eCRF page 'Appearance and Function of Eyelids' is answered 'Yes'.
- Incidence of proven punctual occlusion, which will be considered as present, if the question 'Is there evidence of punctual occlusion?' on the eCRF page 'Appearance and Function of Eyelids' is answered 'Yes'.
- Incidence of punctual plugs, which will be considered as present, if the box 'Punctual plugs' is ticked on the eCRF page 'Appearance and Function of Eyelids'.

- Incidence of thermal or surgical occlusion, which will be considered as present, if the box 'Thermal or surgical occlusion' is ticked on the eCRF page 'Appearance and Function of Eyelids'.
- Incidence of Other punctual occlusion, which will be considered as present, if the respective 'Other' box is ticked on the eCRF page 'Appearance and Function of Eyelids'.

8 Analysis Methods

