9.6.4 Slit Lamp Examination

All grading assessments of different eye structure (excluding assessment for Other structures) will by will be summarized descriptively by treatment group and study visit for the Main Eye as well as the Secondary eye. This analysis will be performed on the SAF.

All data recorded on the eCRF page 'Slit Lamp Examination (Biomicroscopy)' will be listed.

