9.6.5 External Ocular Examinations

All evaluations of the motility of extraocular muscle Right and Up, Right, Right and Down, Left and Up, Left, Left and Down will by will be summarized descriptively by treatment group and study visit for the Main Eye as well as the Secondary Eye. This analysis will be performed on the SAF. These data will also be listed.

Incidences of proven eyelid deformity/abnormality, abnormal motor function of eyelids, corneal exposure in case of closed eyelid, proven punctual occlusion, punctual plugs, thermal or surgical occlusion or other punctual occlusion will be presented by treatment group and study visit for the Main Eye as well as for the Secondary Eye.

Incidences will be calculated as number and percentages of affected patients. The analysis will be performed on the SAF. Moreover, these date will be listed.

10 References

1. Holladay, JT (1997) Proper Method for Calculating Average Visual Acuity. *Journal of Refractive Surgery*, 13, pp. 388-391.
2. Lemp MA. Report of the National Eye Institute/Industry Workshop on clinical trials in dry eye. *CLAO J*1995, 21(4):221–32.

11 Tables, Listings and Figures

Details on Tables and Listings (TLFs) will be provided in a separate document and are attached as appendix to this SAP.

TLF Number	Title
List of Tables	
Table 14.1-1.1	Summary of Patient Disposition
Table 14.1-1.2	Summary of Study Discontinuation (Enrolled Set)
Table 14.1-2.1	Summary of Protocol Deviations (FAS)
Table 14.1-3.1	Summary of Demographic Data (Enrolled Set)
Table 14.1-4.1	Summary of History of Corneal Surgery (SAF)
Table 14.1-5.1	Summary of Medical History (SAF)
Table 14.1-6.1	Summary of Prior Medications (SAF)
Table 14.1-6.2	Summary of Concomitant Medications (SAF)
Table 14.1-7-1	Summary of Treatment Compliance (FAS)
Table 14.2-1.1	Summary of SANDE Scores at Week 8 (LOCF) (FAS)
Table 14.2-1.2	Summary of Change from Baseline of SANDE Scores at Week 8 (LOCF) (FAS)
Table 14.2-1.2.1	Summary of Change from Baseline of SANDE Scores at Week 8 in Subgroups (LOCF) (FAS)
Table 14.2-1.3	Summary of SANDE Scores at Week 8 (LOCF) (PPS)
Table 14.2-1.4	Summary of Change from Baseline of SANDE Scores at Week 8 (LOCF) (PPS)
Table 14.2-2.1	Summary of SANDE Scores by Visit (Observed) (FAS)
Table 14.2-2.2	Summary of Change from Baseline of SANDE Scores by Visit (Observed) (FAS)
Table 14.2-3.1	Summary of Corneal Staining at Week 8 (LOCF) (FAS)

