Table 14.3.3-2.2	Summary of Change from Baseline of LogMAR (SAF)
Table 14.3.4-1.1	Summary of Slit Lamp Examination (SAF)
Table 14.3.5-1.1	Summary of Motility of Extraocular Muscle (SAF)
Table 14.3.5-2.1	Summary of Appearance and Function of Eyelid (SAF)
List of Listings	
Listing 16.1.7-1.1	Randomized Allocation to Treatment and assigned kit numbers (Enrolled Set)
Listing 16.2.1-1.1	Listing of Screening Failure
Listing 16.2.1-1.2	Listing of Study Completion (Enrolled Set)
Listing 16.2.2-1.1	Listing of Protocol Deviations (Enrolled Set)

TLF Number	Title
Listing 16.2.2-1.2	Listing of Inclusion Criteria Deviations at Baseline (Enrolled Set)
Listing 16.2.2-1.3	Listing of Exclusion Criteria Deviations at Baseline (Enrolled Set)
Listing 16.2.3-1.1	Listing of Allocation to Analysis Sets (Enrolled Set)
Listing 16.2.4-1.1	Listing of Demographic Data (SAF)
Listing 16.2.4-2.1	Listing of History of Corneal Surgery (SAF)
Listing 16.2.4-3.1	Listing of Medical History (SAF)
Listing 16.2.4-4.1	Listing of Prior and Concomitant Medications (SAF)
Listing 16.2.5-1.1	Listing of Exposure and Treatment Compliance (SAF)
Listing 16.2.5-1.2	Listing of Treated Eyes, Self Administration and Diary summary information (SAF)
Listing 16.2.5-1.3	Listing of Patient Diary Entries (SAF)
Listing 16.2.6-1.1	Listing of SANDE Scores (FAS)
Listing 16.2.6-2.1	Listing of Ocular Surface Staining: Corneal Staining (FAS)
Listing 16.2.6-2.2	Listing of Ocular Surface Staining: Conjunctival Staining (FAS)
Listing 16.2.6-2.3	Listing of TFBUT and Corneal Sensitivity (FAS)
Listing 16.2.7-1.1	Listing of Adverse Events (SAF)
Listing 16.2.7-1.2	Listing of TEAEs Leading to Premature Withdrawal of Study Treatment (SAF)
Listing 16.2.7-1.3	Listing of TEAEs Leading to Study Treatment Interruption (SAF)
Listing 16.2.7-1.4	Listing of TEAEs Related to Study Treatment (SAF)
Listing 16.2.7-1.5	Listing of Serious AEs (SAF)
Listing 16.2.7-1.6	Listing of Serious TEAEs Related to Study Treatment (SAF)
Listing 16.2.7-1.7	Listing of Fatal TEAEs (SAF)
Listing 16.2.7-2.1	Listing of Action taken due to AEs (SAF)
Listing 16.2.7-2.2	Listing of Corrective Procedures Related to AEs (SAF)
Listing 16.2.8-1.1	Listing of Urine Pregnancy Test (Females in SAF)
Listing 16.2.9-1.1	Listing of BCDVA assessments (SAF)
Listing 16.2.9-1.2	Listing of BCDVA score, Snellen Scale and logMAR (SAF)
Listing 16.2.10-1.1	Listing of Slit Lamp Examination – Part I (SAF)
Listing 16.2.10-1.2	Listing of Slit Lamp Examination – Part II (SAF)

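### Slit-lamp, motility and eyelid safety findings are summarised only by visit, so the planned tables cannot separate new from resolved findings, and seven eyelid and punctal items labelled as incidence are prevalences

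*SAP*

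**What the plan says.** **Slit lamp.** SAP 7.2.8 states "All grading assessments of different eye structures will be evaluated as collected on the eCRF at Baseline Visit" and at Weeks 4, 8 and 12. SAP 9.6.4 has the grades "summarized descriptively by treatment group and study visit for the Main Eye as well as the Secondary eye", on the Safety Set. The table list in SAP 11 has one slit-lamp summary (14.3.4-1.1).

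**Motility.** SAP 7.2.8 takes Normal/Abnormal for each field of movement "as documented at the eCRF at Baseline Visit, Week 4, Week 8 and Week 12". There is one table (14.3.5-1.1).

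**Eyelids and puncta.** SAP 7.2.8 defines seven items, each named as an incidence: lid deformity or abnormality, abnormal lid motor function, corneal exposure with closed lids, punctal occlusion, plugs, thermal or surgical occlusion, and other occlusion. The first begins "Incidence of proven eyelid deformity/abnormality, which will be considered as present, if the question 'Evidence of eyelid deformity or abnormality" and is met by a Yes answer. The plug item reads "Incidence of punctual plugs, which will be considered as present, if the box" for plugs is ticked. None requires that the finding was absent at Baseline. Under SAP 9.6.5 the items "will be presented by treatment group and study visit for the Main Eye as well as for the Secondary Eye", as the number and percentage of affected patients in the Safety Set. There is one table (14.3.5-2.1).

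**Contrast.** SAP 9.6.3 plans absolute values and changes from baseline for BCDVA and logMAR, with separate change tables (14.3.3-1.2 and 14.3.3-2.2).

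**The concern.** Counts by visit give the net state of the group. A percentage that does not move between Baseline and Week 8 may mean that nothing happened, or that some eyes cleared while as many others became abnormal. The distinction matters here because patients enter within 6 months of cataract or refractive surgery (Protocol 5.2, criterion 2a). Some signs may be present at Baseline and resolve during the study. Faster recovery on rhNGF is also what the trial hopes to see (Protocol 1.2 and 1.3).

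For the seven eyelid and punctal items the label adds to the difficulty. A plug or lid deformity that was there at Baseline and persists appears in the incidence figure at Weeks 4, 8 and 12. The denominator is not limited to eyes that were free of it. Read literally, the Week 8 figure would be taken as new findings on treatment, when it is a point prevalence.

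**Working it through.** The plan gives no baseline prevalence, recovery rate or new-onset rate for these findings, so there is no figure of its own to reproduce. The first step is textual; the rest is illustration.

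**1. Definitions, outputs and table list.**

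| Assessment | Evaluated as | Called incidence? | Baseline comparison in SAP text or table list |
|---|---|---|---|
| Slit-lamp grades | grade at each visit | no | none |
| Motility | Normal/Abnormal at each visit | no | none |
| Eyelid and punctal items (7) | present at the visit | yes | none |
| BCDVA, logMAR | value and change | no | change tables |

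**2. Within one arm.** Let *p0* be the share of eyes abnormal at Baseline, *r* the share of those that resolve, and *w* the share of baseline-normal eyes that become abnormal. Then

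prevalence at visit = *p0*(1 − *r*) + (1 − *p0*)*w*,

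and the net change is zero when *w* = *p0* *r* / (1 − *p0*).

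Assume *p0* = 20% and *r* = 50%, with one eye for each of 120 rhNGF patients:
- Abnormal at Baseline: 0.20 × 120 = 24. Normal: 96.
- Resolved: 0.50 × 24 = 12.
- New-onset share giving zero net change: 0.20 × 0.50 / 0.80 = 12.5%, or 12 of 96.
- The by-visit table shows 24/120 (20%) both times. A shift table shows 12/96 new and 12/24 resolved.

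The new-onset share fully offset in this way runs from 1.3% (*p0* 5%, *r* 25%) to 50% (*p0* 40%, *r* 75%).

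**3. Between arms.** With equal *p0* by randomisation,

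difference in prevalence = (1 − *p0*)(*w*A − *w*V) − *p0*(*r*A − *r*V),

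where A is rhNGF and V is vehicle. Assume *p0* = 20%, *w*A = 10% and *w*V = 2%, a true new-onset difference of 8 points among eyes free at Baseline.

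| Recovery, rhNGF / vehicle | Prevalence, rhNGF | Prevalence, vehicle | Difference |
|---|---|---|---|
| 50% / 50% | 0.10 + 0.08 = 18.0% | 0.10 + 0.016 = 11.6% | +6.4 points |
| 75% / 50% | 0.05 + 0.08 = 13.0% | 0.10 + 0.016 = 11.6% | +1.4 points |
| 75% / 25% | 0.05 + 0.08 = 13.0% | 0.15 + 0.016 = 16.6% | −3.6 points |

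With equal recovery the second term vanishes and the difference is only scaled by 1 − *p0*: 0.80 × 8 = 6.4. It vanishes when *r*A − *r*V = (1 − *p0*)(*w*A − *w*V)/*p0*, which here is 0.80 × 0.08 / 0.20 = 32 points. Across *p0* of 10% to 40% and the same three recovery pairs, the difference runs from +7.2 to −15.2 points.

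**The case against.** The other side has several good points.

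- **New harm has its own route.** The safety endpoint is TEAEs. Protocol 11.3 has the investigator review changes in every protocol-specific ocular parameter and report clinically relevant untoward change as an AE, whatever its cause. This stands and limits the point. It leaves out changes not judged clinically relevant. Also, Protocol 10.6 counts events that occur or worsen after first dose as TEAEs, while SAP 7.2.8 refers to events that started on or after first dose.
- **Baseline is displayed and eye-level data are listed** (SAP 9.6.4 and 9.6.5; Listings 16.2.10 and 16.2.11). Carried-over findings can therefore be seen in aggregate, and a reader could match eyes by hand. This stands, but group margins still do not separate new from resolved findings.
- **Other objective eye data are compared with baseline.** Staining, TFBUT and corneal sensitivity have change tables (14.2-4.2, 14.2-5.2, 14.2-6.2). They are efficacy outputs on the FAS, but ocular surface worsening would show there. A reader might infer that visual acuity is the only objective eye measure compared with baseline; that is not so.
- **The word incidence is used loosely throughout.** SAP 8.1 applies it to medical history and concomitant medications too, and SAP 9.6.5 says how it is calculated. That lowers the risk of misreading, but a clearer label is still warranted. A reader might infer that slit-lamp and motility results are also called incidences; they are not.
- **Recovery from baseline signs is not documented.** Exclusion criteria 1 and 2 (Protocol 5.3) remove other ocular disease needing topical treatment and active inflammation unrelated to dry eye. Plugs, surgical occlusion and motility are unlikely places for recovery to offset irritation. This limits the point mainly to graded signs such as erythema.
- **By-visit frequencies are a legitimate descriptive choice** for ordinal grades in an exploratory study, and the mock shells are a separate document not seen here. Both are fair. The SAP text nevertheless defines no change or new-finding variable for a shell to show.

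**Conclusion.** The point holds in a limited form. For slit lamp, motility and eyelids, neither the SAP text nor its table list contains a within-eye comparison with Baseline. The seven eyelid and punctal incidences are presence-at-visit counts over the Safety Set. What is lost is the separation of new from resolved findings, chiefly for changes not judged clinically relevant.

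A reader might go further and infer that recovery after surgery will cancel drug harm and make the arms look alike. The documents do not support that. Randomisation keeps the comparison of by-visit prevalence informative, and equal recovery only dilutes a difference (8 to 6.4 points in the example). Hiding or reversing it needs recovery to differ by arm, by 32 points in that example. This is plausible if rhNGF works, but no passage shows it, and every rate used here is an assumption.

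Severity is minor. The formal safety endpoint is TEAEs, and no efficacy analysis, test or sample size is affected.

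**What to change.** In SAP 7.2.8, 9.6.4 and 9.6.5, before unmasking:

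1. Rename the seven eyelid and punctal items as presence (prevalence) at visit.
2. For eyelid and motility items, add by arm the number and percentage newly abnormal among treated eyes free of the finding at Baseline.
3. For each graded slit-lamp structure, add one shift table by arm: Baseline grade against worst post-baseline grade through Week 8, and again through Week 12, with the number of treated eyes worsening by at least one grade. State whether unscheduled visits count towards the worst grade, since SAP 7.1 now reserves them for imputation.
4. Add these outputs to the table list in SAP 11 and to the shells.

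The cost is SAP wording and a few extra descriptive tables from data already collected. No new assessments are needed. The by-visit tables can stay.

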8.1 General Methods

All analyses for this exploratory study will be done by using appropriate descriptive statistics by study group. All results will be summarized in tables. Patient individual data will be provided in Listings. No graphs are envisaged for this study.

For **continuous variables**, the mean, standard deviation, coefficient of variation (in %), minimum, median and maximum will be presented, together with the total number of observations and the number of missing and non-missing values. Unless otherwise specified minimum and maximum values will be reported to the same number of decimal places as the recorded measurements, mean and median are reported to one more decimal place and standard deviation one additional decimal place more than the mean.

For **categorical variables**, absolute and relative frequencies will be reported. Relative frequencies will be based on all observations and reported as a percentages to one decimal place. Unless otherwise specified, percentages will be based on the number of patients in considered analysis set including also percentages for missing categories. Only categories with non-null values will be presented in summary tables.

Incidences like adverse events, medical history and concomitant medications will be reported on a subject basis. The percentages will be calculated using the number of patients in the considered analysis data set.

8.2 Specific Methods for Efficacy Analyses

As a general principle, all efficacy analyses will be performed on a patient-level, considering the Main Eye for the analysis of Co-Primary and Secondary efficacy endpoint. Efficacy data in Secondary eye will be present as descriptive summaries and listed.

For the primary and co-primary efficacy endpoints, mean change from baseline will be compared between treatment groups. The null hypothesis will be tested that there is no difference between rhNGF and vehicle in the mean overall CFB between both treatments:

$$H_0: \mu_{\text{rhNGF}} = \mu_{\text{Vehicle}}$$

$$H_1: \mu_{\text{rhNGF}} \neq \mu_{\text{Vehicle}}$$

Where μ is the mean change from baseline at considered visit within the given treatment.

This hypothesis will be tested exploratory at a 5% level of significance with an Analysis of the Covariance (ANCOVA) with treatment, respective baseline value and eye subgroup (1 vs 2 study eyes treated) in the model.

The Least-squares means estimate of the treatment effect and the treatment group difference (both with 95% confidence intervals) will be reported. P-values will be rounded to three decimal places. If a p-value is less than 0.001 it will be reported as “<0.001”. Due to the high numbers of observations, the assumption of normality is assumed.

The ANCOVA analysis will be performed for the following endpoints:

- Change from Baseline in SANDE Frequency and Severity Score at Week 8 (LOCF) for the FAS as exploratory primary efficacy analyses
- Change from Baseline in SANDE Frequency and Severity Score at Week 8 (LOCF) for the PPS as supportive to primary efficacy analyses

- Change from Baseline in SANDE Frequency and Severity Score (without imputation) at Week 8 for the FAS as supportive to primary efficacy analyses
- Change from Baseline in Corneal Staining at Week 8 (LOCF) for the FAS as exploratory to co-primary efficacy analyses
- Change from Baseline in Corneal Staining at Week 8 (LOCF) for the PPS as supportive to co-primary efficacy analyses
- Change from Baseline in Corneal Staining (without imputation) at Week 8 for the FAS as supportive to co-primary efficacy analyses

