### **5.2 Inclusion criteria**

To be enrolled in this study, patients must fulfil all these criteria:

1. Male or female  $\geq 18$  years old
2. Patients who are characterized by the following clinical features:
  - a. History of cataract or refractive corneal surgery in the study eye(s) in the previous 6 months;
  - b. Mean Symptom Assessment in Dry Eye (SANDE) score for severity and frequency of at least 30 at baseline
3. The same eye (study eye) must fulfill all the above criteria
4. Best corrected distance visual acuity (BCDVA) score of  $\geq 0.1$  decimal units in both eyes at the time of study enrolment
5. Female patients must have negative pregnancy urine test if at childbirth potential.
6. Only patients who satisfy all requirements for informed consent may be included in the study. Written Informed Consent must be obtained before the initiation of any study-specific procedures.
7. Patients must have the ability and willingness to comply with study procedures.

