## **8 ASSIGNMENT OF STUDY TREATMENT**

### **8.1 Randomization**

After obtaining informed consent a consecutive screening number will be assigned to each patient according to the sequence of study entry, from S001 onwards (S002, S003 etc.). After confirming eligibility for the study, patient will be randomized (2:1 to rhNGF eye drops solution at 20 µg/ml (120 patients) or vehicle eye drops solution (60 patients) to be administered 6 times per day per study eye (or both eyes if applicable) for 8 weeks) and allocated with a consecutive randomization number of the randomization list starting with 001 onwards (002, 003 etc.).

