3.1 Study Objectives

The primary objective of this study is to assess efficacy and safety of rhNGF when administered as eye drops to patients after cataract and refractive surgery.

The objectives are reflected by the endpoints as stated in section 3.4.

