3.2 Study Design

This is a Phase II, single-centre, randomized, double-masked, parallel-arm, vehicle-controlled trial, designed to evaluate the preliminary efficacy and safety of rhNGF eye drops at 20 µg/ml concentration administered six times daily for 8 weeks in patients who underwent cataract and corneal refractive surgery, both known to damage the corneal sensory nerve plexus.

Eligible patients will be randomized 2:1 to either rhNGF eye drops 20 µg/ml (120 patients) or vehicle (60 patients) six times daily and treated for 8 weeks:

Group 1: rhNGF 20 µg/mL: *One drop (40 µL) corresponding to 0.80 µg of rhNGF will be instilled into each eligible eye six times a day (every 2h), for a total daily dose of 9.6 µg (both eyes, if applicable), for 56 consecutive days..*

Group 2: Vehicle: *One drop (40 µL) will be instilled into each eligible eye six times a day (every 2h).*

[figure not shown]
In all patients, both eyes will be treated, if meet the eligibility criteria. If only one eye is eligible, then only that eye will be treated.

In the 4 week follow up no further treatment is planned except artificial tears, per Investigator decision. Administration of such medications will be recorded in eCRF (number of drops per day).

Drop-Outs after randomization will not be replaced.

The study flow chart is given below:

Figure 3.2.1 Study flow chart

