6.2 Subgroup Definitions

For supportive efficacy analysis, subgroup of patients with '1 study eye only' vs. '2 study eyes' will be utilized.

7 Definition of Time Points and Analysis Variables

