7.2.3 History of Corneal Surgery and other Medical History

The details of Corneal Surgery are recorded on the eCRF page "Medical history".

The following parameters will be analysed:

- Patients with previous cataract surgery (Yes/No)
- Eyes involved in previous cataract surgery per patient (Right Eye only, Left Eye only, Both Eyes)
- Patients with previous refractive surgery (Yes/No)
- Eyes involved in previous refractive surgery per patient (Right Eye only, Left Eye only, Both Eyes)
- Patients with previous LASIK surgery (Yes/No)

- Eyes involved in previous LASIK surgery per patient (Right Eye only, Left Eye only, Both Eyes)

Identification of study eye(s) ('Right eye', 'Left eye') is recorded on the "Study Eye" eCRF page and will be analyzed as derived categories 'Both Eyes', 'Left Eye only', 'Right Eye only'.

All other medical history is recorded on the "Medical history" eCRF page.

Medical history contains information about conditions that a patient might have suffered prior to Baseline visit, or conditions that are ongoing at the time of the Baseline visit.

The medical history terms as specified by the investigator will be coded to a Preferred Term (PT) and a System Organ Class (SOC) using the Medical Dictionary for Regulatory Activities (MedDRA) thesaurus.

In the event that coding information will not be available for a specific medical history record, the record will be presented as 'Uncodable Record'. However, for final TLFs it is anticipated that all medical history records are coded.

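### Surgery type and time since surgery enter neither the efficacy model nor the subgroups, which costs some precision, protection against chance imbalance, and any view of consistency across the two operations.

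*SAP*

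**What the plan says.** **Entry.** Protocol 5.2 requires "History of cataract or refractive corneal surgery in the study eye(s) in the previous 6 months". This sets an upper limit and no lower one, and either operation qualifies. Exclusion 5 in Protocol 5.3 applies a 90-day limit to ocular surgery but exempts these two procedures.

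**Allocation.** Under Protocol 8.1 each patient is "allocated with a consecutive randomization number of the randomization list starting with 001 onwards". Protocol 8.3 adds that kits are used in numerical order. Neither section states a stratification factor.

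**Model.** The ANCOVA in SAP 8.2, used for SANDE frequency, SANDE severity and corneal staining, contains "treatment, respective baseline value and eye subgroup (1 vs 2 study eyes treated) in the model".

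**Subgroups.** SAP 6.2 opens "For supportive efficacy analysis, subgroup of patients with" and goes on to name one versus two study eyes. No other subgroup is defined.

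**Baseline tables.** SAP 7.2.3 and 9.3.2 summarise cataract, refractive and LASIK history, and the eyes involved, by treatment group. Time since surgery is neither derived nor tabulated, and surgery type appears in no efficacy analysis.

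**Objective and status.** SAP 3.1 states one pooled objective, "to assess efficacy and safety of rhNGF when administered as eye drops to patients after cataract and refractive surgery". SAP 3.7 and 8.2.1.3 label all inference exploratory.

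**The concern.** Protocol 1.2 and 1.3 rest the rationale on surgical damage to the corneal nerve plexus and its restoration. On that reasoning, which operation a patient had and how long ago are natural candidates to predict change over 8 weeks. Both are fixed before randomisation, so both may be adjusted for.

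Three things are at stake:

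- Variation in change that these factors could explain stays in the error term.
- If the arms happen to differ on them, the estimate carries that difference.
- No planned table shows the treatment difference by operation. The SAP does provide for repeating the ANCOVA by number of study eyes (9.5.1 and 9.5.2), but not by the two operations that define the population.

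**Working it through.** **1. The plan's own figure.** Inputs from SAP 3.6: two-sided alpha 0.05, power 80%; SANDE difference 10, SD 20; corneal staining difference 1.0, SD 2.2; dropout 5%; ratio 2:1.

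Per arm at 1:1, n = 2 × [SD × (1.960 + 0.842) / difference]²:

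- SANDE: 62.8, so 63. At 2:1: 0.5 × 63 × 3 = 94.5 and 0.5 × 63 × 1.5 = 47.25. Divided by 0.95: 100 and 50.
- Staining: 75.98, so 76. At 2:1: 114 and 57. Divided by 0.95: 120 and 60.

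The planned 180 is reproduced. With 114/57 evaluable patients, power is 80.0% for staining and 86.9% for SANDE.

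The documents give no surgery mix, no distribution of time since surgery and no recovery rates. Everything below rests on assumptions, shown as ranges where they drive the result.

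**2. Is the comparison biased?** A simulation (4,000 runs, 114/57) assumed a 70/30 surgery mix, a 10-point difference in SANDE recovery between operations, a further 3 points per month since surgery (uniform over 0 to 6 months), and a total SD of 20. The two factors then carry 100 × 0.21 + 9 × 3 = 48 of the variance of 400, or 12%. The reduced model held treatment and baseline; the full model added both factors.

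- Type I error: 5.2% in each model.
- Mean estimate when the true effect is −10: −10.0 in each model.
- SE of the treatment effect: 3.2 without the factors, 3.0 with them.
- Power: 87.0% without, 90.3% with.

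So there is no bias on average, and a modest loss of precision.

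**3. Chance imbalance at 120/60, without stratification.** SE of the difference in proportions = √[p(1 − p)(1/120 + 1/60)].

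| Majority type (assumed) | SE, points | Chance of a gap above 10 points |
|---|---|---|
| 50% | 7.9 | 21% |
| 70% | 7.2 | 17% |
| 80% | 6.3 | 11% |
| 90% | 4.7 | 3.5% |

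If the operations differ in SANDE recovery by 5 to 20 points (assumed), a 10-point gap moves the treatment difference by 0.10 × 5 = 0.5 to 0.10 × 20 = 2.0 points, against a planned 10.

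For time since surgery uniform over 0 to 6 months (assumed), the SD is 6/√12 = 1.73 months. The arm means then differ with SE 1.73 × √(1/120 + 1/60) = 0.27 months, or ±0.54 months in 95% of randomisations.

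**4. Power after adjustment at 114/57.** Each planned SD is taken as the residual SD and multiplied by √(1 − R²), where R² is the share of residual variance that the two factors explain.

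| R² (assumed) | Staining | SANDE |
|---|---|---|
| 0 | 80.0% | 86.9% |
| 5% | 82.0% | 88.5% |
| 10% | 84.0% | 90.1% |
| 20% | 88.0% | 93.1% |

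The required sample size does not rise.

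**5. What results by operation can show.** For a type making up 50, 30 or 20% of patients, power to detect the planned difference within that type is 59, 39 or 28% for SANDE and 51, 34 or 24% for staining. At a 50% share (57 versus 28.5), the SANDE interval has half-width 1.96 × 20 × √(1/57 + 1/28.5) = 9.0 points. For the interaction it is √2 times that, 12.7 points.

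**The case against.** **Recovery is already controlled by design.** A reader might infer that natural post-surgical recovery is left uncontrolled. It is not. The trial is randomised, masked and vehicle-controlled, so recovery is balanced in expectation, and the baseline term takes up part of the rest. Chance imbalance is also reflected in the ordinary standard error. This stands: adjustment narrows that error and removes an imbalance actually seen, but it does not repair a biased comparison.

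**The assumed vehicle response.** A reader might take the planned vehicle changes (−20 of −30 for SANDE, −2.9 of −3.9 for staining) as the share of improvement due to surgical recovery. The documents never attribute them to that. Regression to the mean after the SANDE entry threshold, lubrication or a placebo response could produce the same figures. A mean change also does not show how much recovery varies between patients.

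**The objective is pooled.** A reader might say that the stated objective needs an effect for each operation. It does not: SAP 3.1 names the two operations together and sets no objective for either one. Consistency across them is useful to know in a Phase II study of preliminary efficacy, but it is not a promised result.

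**Partly visible already.** Surgery type is tabulated by arm, so an imbalance in type would be seen. Exclusions 1 and 2 in Protocol 5.3 may remove some very early patients, although they set no minimum time. The lack of stratification is read from silence in Protocol 8.1 to 8.3.

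**Exploratory status.** All testing is exploratory, which lowers the stakes. It does not remove the point, because covariates and subgroups chosen after unmasking would carry less weight than ones fixed now.

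**Conclusion.** The omission is certain; its impact is moderate and rests on assumptions. The treatment comparison remains valid on average. What the plan gives up is:

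- some precision, worth 2 to 8 points of power for staining and about 1.6 to 6.2 for SANDE if the factors explain 5 to 20% of residual variance;
- protection against a chance gap in surgery mix, which could move the SANDE difference by 0.5 to 2.0 points under the assumptions shown;
- any estimate of whether the effect is similar after the two operations.

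Staining gains most, since its planned power is exactly 80%. If one operation dominates enrolment, or the factors predict little, the gain is small. Neither document allows a firmer figure, and nothing here invalidates the planned analysis.

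**What to change.** Amend the SAP before unmasking.

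1. **SAP 8.2.** Add surgery type and days from the qualifying surgery to Baseline to the ANCOVAs, with a coding rule for each endpoint.
   - *Staining:* use the Main Eye's qualifying operation and, if that eye had both, the more recent one.
   - *SANDE:* SAP 7.2.7 records one score for both eyes together, so use a patient-level rule: cataract only, refractive only, or both, with days from the most recent qualifying surgery.
   - *Definitions:* state that LASIK counts as refractive, and that only operations within the 6-month window qualify, since the history items in SAP 7.2.3 carry no time limit.
   - *Date:* SAP 7.2.3 does not list the surgery date. Take it from the record used to verify inclusion 2a, and confirm that it is in the database.
2. **SAP 9.3.2.** Tabulate time since surgery by arm beside surgery type.
3. **SAP 6.2 and 9.5.** Add surgery type as a subgroup. Always report the treatment difference with its 95% CI in each type, and the treatment-by-type interaction, labelled as estimates and not tests.

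The cost is SAP wording, one derived variable, one extra baseline row, a subgroup table and 2 to 3 degrees of freedom. Subgroup intervals will be wide, and the text should say so.
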